#### 4.2 Dose escalation guidelines

No doses escalation will be permitted on this study.

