##### General guidelines for dose modifications

- For grade 1 and tolerable grade 2 treatment-related toxicities, patients are encouraged to continue at the current dose of study treatment. For intolerable grade 2 treatment-related toxicities, dosing should be interrupted until resolution to grade 1 or lower followed by dose reduction to the next dose level.
- For grade 3 or grade 4 treatment-related toxicity that is not considered by the investigator to be life-threatening, patients should interrupt study treatment until resolution to grade 1 or lower; then study treatment may continue following a dose reduction to the next dose level, if, in the opinion of the Investigator, the patient continues to experience clinical benefit. For any grade 3 or 4 treatment-related toxicity that is considered by the investigator to be life-threatening, permanently discontinue study treatment.

More detailed ceritinib dose modification guidelines are described in Section 4.3.1 respectively for selected toxicities.

All dose modifications, interruptions or discontinuations must be based on the worst preceding toxicity as graded by the NCI Clinical Toxicity Criteria version 4.03.

Patients whose treatment is interrupted or permanently discontinued due to an AE must be followed until resolution or stabilization of the event. Patients requiring interruptions greater than 1 cycle (28 days)

should be discontinued from ceritinib treatment unless the treating physician and Principle investigator agree that the patient should resume treatment.

All patients will be followed for safety until 30 days after the last dose of ceritinib.

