**Table 4-2 Dose reduction steps for ceritinib**

Ceritinib dose levels	Dose* and schedule
Starting dose level	450 mg QD continuously
Dose level - 1	300 mg QD continuously
Dose level – 2**	150 mg QD continuously

\*Dose reduction will be based on the worst preceding toxicity as per NCI-CTCAE version 4.03.

\*\*Dose reduction below 150 mg/day is not allowed. If a dose reduction below 150 mg/day is required, the patient will be permanently discontinued from ceritinib.

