	
Repeat ECGs 7 days and 14 days (and then every 21 days) after dose resumption for all patients who had therapy interrupted due to QTc ≥ 501 ms.
 
If QTc of ≥ 501 ms recurs, interrupt ceritinib treatment. If QTc returns to ≤ grade 1 (< 481 ms), ceritinib may be reduced again by 1 dose level (i.e., 450 mg QD or 300mg QD). Repeat ECGs as described above.
 
If QTc of ≥ 501 ms recurs after 2nd dose reduction for QTc prolongation, the patient must be discontinued from study.
 
QTc of >480 ms should be reported as an adverse event (AE)

Grade 4 (QTc ≥ 501 or > 60ms change from baseline and Torsades de pointes or polymorphic ventricular tachycardia or signs/symptoms of serious arrhythmia)	Permanently discontinue patient from ceritinib
PULMONARY	

Notes:
 
 
Withhold ceritinib for acute onset of new or progressive unexplained pulmonary symptoms, such as dyspnea, cough and fever and during diagnostic workup for pneumonitis/ILD.
 
During evaluation of potential grade 2, 3, and 4 pneumonitis, if an infectious etiology is confirmed (i.e., pneumonia) and pneumonitis is excluded, then consider resuming ceritinib at current dose level after the pneumonia resolves.
 
	
PNEUMONITIS	
Any Grade treatment-related ILD/pneumonitis	Permanently discontinue patient from ceritinib.
BRADYCARDIA	
Grade 1	
Omit dose until recovery to asymptomatic bradycardia or to a heart rate ≥ 60 bpm
 
Evaluate concomitant medications known to cause bradycardia and adjust the dose of ceritinib

Grade 2	
Omit dose until recovery to asymptomatic bradycardia or to a heart rate ≥ 60 bpm
 
Evaluate concomitant medications known to cause bradycardia and adjust the dose of ceritinib

Grade 3 Grade 4 (in patients taking a concomitant medication also known to cause bradycardia or a medication known to cause hypotension)	
Omit dose until recovery to asymptomatic bradycardia or to a heart rate ≥ 60 bpm
 
If the concomitant medication can be adjusted or discontinued, resume ceritinib at ↓ 1 dose level with frequent monitoring

Grade 4 (in patients who are not taking a concomitant medication also known to cause bradycardia or known to cause hypotension)	Permanently discontinue ceritinib

Worst toxicity (CTCAE 4.03 Grade)*	Dose Modifications for Ceritinib
PANCREATIC	
Amylase and/or lipase elevations (in the absence of clinical symptoms)	

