### 7.1.2 Special Warnings and Precautions for Use:

Cardiac: symptomatic bradycardia can occur with heart rate <50/min. If possible, will avoid concurrent use of agents that may cause bradycardia (eg, beta blockers, nondihydropyridine calcium channel blockers, clonidine, digoxin). Will monitor heart rate and blood pressure regularly. Dose will be held for symptomatic bradycardia.

QTc prolongation: QTc interval prolongation has occurred in clinical studies, and may be concentration-dependent. Will periodically monitor ECG and electrolytes in patients with heart failure, bradyarrhythmias, electrolyte abnormalities, or who are taking medications known to prolong the QTc interval. May require treatment interruption, dosage reduction, or discontinuation. Will permanently discontinue in patients who develop QTc interval prolongation in combination with torsades de pointes or polymorphic ventricular tachycardia or signs/symptoms of serious arrhythmia.

Gastrointestinal toxicity: Diarrhea, nausea, vomiting, or abdominal pain occurred in the majority of patients in clinical trials; over one-third of patients required dose reductions due to severe or persistent gastrointestinal toxicity. Symptomatic management will be with antiemetics and antidiarrheals.

Hepatotoxicity: Hepatotoxicity has been observed in patients treated with ceritinib in clinical trials, including ALT levels >5 times ULN in over one-quarter of patients.

Hyperglycemia: Hyperglycemia, including grade 3 and 4 toxicity, has been observed in ceritinib-treated patients. Close monitoring of blood sugars in patients with baseline random blood sugar greater than 180, with addition of insulin or other medication to correct hyperglycemia.

Pulmonary toxicity: Severe and life-threatening interstitial lung disease (ILD)/pneumonitis (some fatal) may occur. Monitor for signs/symptoms of pulmonary toxicity; permanently discontinue in patients diagnosed with treatment related ILD/pneumonitis.

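### Table 4-3's Grade 1 and Grade 2 bradycardia rows call for a ceritinib dose adjustment on grade alone, with no symptom condition and no dose step

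*Combined protocol and SAP*

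**What the plan says.** Table 4-3 (Section 4.3.1) gives identical instructions for Grade 1 and Grade 2 bradycardia. The first is "Omit dose until recovery to asymptomatic bradycardia or to a heart rate ≥ 60 bpm". The second is "Evaluate concomitant medications known to cause bradycardia and adjust the dose of ceritinib". Neither row mentions symptoms as a trigger, and neither gives a direction or size for the adjustment.

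Four other places bear on this:

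- Section 4.3, general guidelines: "For grade 1 and tolerable grade 2 treatment-related toxicities, patients are encouraged to continue at the current dose of study treatment". For intolerable Grade 2 events, "dosing should be interrupted until resolution to grade 1 or lower followed by dose reduction to the next dose level". The section then hands over: "More detailed ceritinib dose modification guidelines are described in Section 4.3.1 respectively for selected toxicities". Section 4.3.2 likewise sends the reader to Table 4-3 for dosing adjustments.
- Section 4.2: "No doses escalation will be permitted on this study".
- Table 4-2: dose levels of 450, 300 and 150 mg once daily.
- Section 7.1.2, cardiac precaution: "Dose will be held for symptomatic bradycardia". It mentions no dose reduction for bradycardia, although the QTc paragraph that follows it does list reduction as an option.

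**The concern.** The two rows act on the mildest grades, yet they are less precise than the row for the most severe ones. The Grade 3/4 row for patients on a contributing co-medication names a one-level reduction and makes it conditional on that medication being adjustable. The Grade 1 and Grade 2 rows say only that the dose is to be adjusted.

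A clinician who follows the row to the letter could cut an active anticancer drug in a patient who feels well. Another, reading Section 7.1.2, could leave the dose alone. Such patients can come to light in routine follow-up: pulse is measured at scheduled visits and ECGs recur at even-numbered cycles (Tables 5-1 and 5-4). Bradycardia is also listed as an adverse event of special interest in Section 7.3.2, so consistent handling matters for the safety description. Sample size, power and the planned analyses are not touched.

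**Working it through.** The plan gives no figure to reproduce here. The check is a comparison of texts, plus one piece of arithmetic.

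**Step 1: what the row does to an asymptomatic patient.** The hold ends when bradycardia is asymptomatic or the heart rate reaches 60 bpm. The two release conditions are joined by *or*, so a patient with no symptoms meets the first at once. The hold has no duration. The dose-adjustment sentence carries no such test and remains in force.

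**Step 2: which direction the adjustment can take.** Section 4.2 rules out escalation. An adjustment from the starting dose can therefore only go down.

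**Step 3: possible size.** The row names no level. If one Table 4-2 step is assumed from the starting dose, the change is 450 to 300 mg: (450 − 300) / 450 = 0.333, a one-third reduction. The default in Section 4.3 for Grade 1 or tolerable Grade 2 treatment-related toxicity is no change.

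**Step 4: comparison with the rest of Table 4-3.**

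- *Separately graded Grade 1 rows other than bradycardia:* neutropenia, thrombocytopenia, total bilirubin, AST/ALT, creatinine, diarrhea, nausea, vomiting, fatigue, QTc, and amylase/lipase. All 11 maintain the dose. Pneumonitis is handled by an any-grade row that states permanent discontinuation outright.
- *Grade 2 rows other than bradycardia:* neutropenia, thrombocytopenia, nausea, fatigue, QTc and amylase/lipase maintain the dose. Bilirubin, AST/ALT and creatinine reduce one level only if resolution takes more than 7 days. Diarrhea and vomiting reduce one level only on recurrence. Wherever a reduction is possible, both the trigger and the step are written down.
- *Bradycardia, Grades 1 and 2:* hold and adjust, with no trigger beyond the grade and no step.

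**Step 5: comparison with Section 7.1.2.** That text is specific to bradycardia, so the rule that a specific instruction overrides a general one does not settle the difference. It makes symptoms the trigger for action; Table 4-3 makes the grade the trigger. For the hold itself the mismatch is only wording in an asymptomatic patient (Step 1). For the dose adjustment it has substance, because Section 7.1.2 calls for none.

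**The case against.** The strongest reply is that Section 4.3 is a general guideline that only encourages continuing, applies only to treatment-related events, and expressly defers to Section 4.3.1. Other Grade 2 rows (bilirubin, AST/ALT, creatinine, diarrhea, vomiting) also depart from it. This stands. A reader might infer that Table 4-3 and Section 4.3 contradict each other; the documents do not support that, because they say which text governs. But if the table governs, its undefined adjustment is the operative instruction, and the other departing rows state their triggers and steps.

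Second, the row may presuppose symptoms, since it speaks of recovery to an asymptomatic state, and the adjustment may be meant to follow from the medication review. Both readings are possible, and the second would leave the step to judgement. Neither is written, and that the row can be read as either a reduction or no change is itself the reason to reword it.

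Third, the documents do not reproduce the CTCAE bradycardia grade definitions, so how symptoms map onto Grades 1 and 2 cannot be checked. This stands as a limit. The row's release test does, however, treat asymptomatic bradycardia as an acceptable state in which to be dosed.

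A reader might also infer that repeated mild events would walk a patient down to the footnote of Table 4-2: "If a dose reduction below 150 mg/day is required, the patient will be permanently discontinued from ceritinib". That requires one mandatory step per event, which the row does not say.

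**Conclusion.** A minor defect in a governing dosing instruction. Read literally, the Grade 1 and Grade 2 bradycardia rows would reduce ceritinib in a patient with asymptomatic bradycardia. That is out of line with the bradycardia precaution in Section 7.1.2, with the Section 4.3 default, and with every other separately graded Grade 1 row in the table.

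The size is at most one possible Table 4-2 step, 450 to 300 mg. The point rests on two assumptions: that asymptomatic bradycardia can be graded 1 or 2, and that a site would read the adjustment as required rather than discretionary. How often this would arise cannot be estimated from the documents.

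**What to change.** Split both rows by symptom status:

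- *Asymptomatic:* maintain the dose level and review co-medication that can slow the heart.
- *Symptomatic:* keep the existing hold with its existing release test, review co-medication, and adjust the ceritinib dose by a step that the sponsor states, for example one level down per Table 4-2.

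Do not add a rule for resuming symptomatic patients at the same dose; that would be a new clinical rule with no basis in the current text. If the sponsor does want a reduction in asymptomatic patients, the rows should say so and name the step.

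The cost is a rewording of two table rows and one sponsor decision on the step, submitted as an ordinary amendment under Section 11.6. Sections 4.3 and 7.1.2 need no edit, and no visits or procedures are added.

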### 4.3.2 Follow-up for toxicities

An unscheduled visit should be performed in all cases below where toxicity monitoring is recommended more frequently than defined by the schedule of assessments (table 5-1).

Ongoing SAEs at the final safety evaluation visit or the end of study treatment visit (whichever is later) should be followed until they improve becoming non serious events, stabilize, or return to baseline levels. Refer to Section 7.2 for SAE.

A summary of selected toxicity follow-up recommendations is listed in table 4-4. For full toxicity information and dosing adjustments please refer to Table 4-3.

**Table 4-4 Follow-up recommendations for specific toxicities**

Toxicity	Follow-up evaluation*
Investigations (hematologic)	Febrile neutropenia, neutropenia or thrombocytopenia $\geq$ CTCAE Grade 3 Test weekly (or more frequently) until $\leq$ Grade 2 Subsequent monitoring must be performed every 3 weeks (or more frequently)
Investigations (hepatic)	Total ALT/AST/total bilirubin Grade 2: Test weekly (or more frequently) until $\leq$ Grade 1 Thereafter, continue to test every 2 weeks (or more frequently) for 2 cycles (8 weeks). If no recurrence of $\geq$ Grade 2 event, continue monitoring every cycle (4 weeks) Total ALT/AST/total bilirubin $\geq$ Grade 3: Test weekly (or more frequently) until $\leq$ Grade 1 Thereafter, continue to test every 2 weeks (or more frequently) for 4 cycles (16 weeks). If no recurrence of $\geq$ grade 2 event, continue monitoring every cycle (4 weeks) Discontinuation due to liver toxicity: Test weekly (or more frequently) until $\leq$ Grade 1 or stabilization
Investigations (renal)	Serum creatinine Grade 2: Test weekly (or more frequently) until Grade 1 Thereafter, test every cycle (4 weeks) Serum creatinine $\geq$ Grade 3: Test twice weekly (or more frequently) until $\leq$ Grade 1 Thereafter, test every cycle (4 weeks)
Investigations (Metabolic)	Hyperglycemia $\geq$ Grade 3 Test weekly (or more frequently) until Grade 1
Investigations (pancreatic)	Amylase/lipase $\geq$ Grade 3: Test weekly (or more frequently) until $\leq$ Grade 1. After resumption of dosing, continue to test weekly for one additional cycle (4 weeks). If no reoccurrence of $\geq$ Grade 2 event, continue monitoring every cycle (4 weeks).

**\*Note:** this table refers only to the evaluation schedule to monitor selected toxicities. Refer to [Table 4-3](#) for dose modifications required for applicable toxicities

#### **4.3.2.1 Guidelines for the follow-up of laboratory hematologic abnormalities**

In case of any occurrence of febrile neutropenia, neutropenia  $\geq$  grade 3, or thrombocytopenia  $\geq$  grade 3, hematology tests must be performed weekly (or more frequently if clinically indicated) until the event resolves to  $\leq$  grade 2. Subsequent monitoring must be performed at least every 4 weeks.

#### **4.3.2.2 Guidelines for the follow-up of laboratory liver abnormalities**

In patients with any clinically relevant laboratory liver abnormality, as defined below, hepatic toxicity monitoring must include **ALL** of the following liver function tests (LFTs): albumin, ALT, AST, total bilirubin (fractionated if total bilirubin  $> 2.0 \times$  ULN), alkaline phosphatase and GGT. Note: for patients with Gilbert Syndrome, total and direct bilirubin must be monitored, but intensified monitoring applies to changes in direct bilirubin only.

In case of any occurrence of ALT/AST/total bilirubin increase to grade 2 the LFTs must be monitored weekly (or more frequently if clinically indicated) until the event resolves to  $\leq$  grade 1. Thereafter monitoring must be continued every 2 weeks (or more frequently if clinically indicated) for two additional cycles (e.g. 8 weeks). If there is no recurrence of  $\geq$  grade 2 ALT/AST/total bilirubin elevations during this period, subsequent monitoring must be performed at least every 4 weeks.

In case of any occurrence of ALT/AST/bilirubin increase to grade 3 or 4, LFTs must be monitored weekly (or more frequently if clinically indicated) until the event resolves to  $\leq$  grade 1. Thereafter monitoring must be continued every 2 weeks (or more frequently if clinically indicated) for four additional cycles (e.g. 16 weeks). If there is no recurrence of  $\geq$  grade 2 ALT/AST/total bilirubin elevations during this period, subsequent monitoring must be performed at least every 4 weeks.

Patients who discontinue ceritinib treatment due to liver toxicity must be monitored weekly (or more frequently if clinically indicated) until the event resolves to  $\leq$  grade 1 or stabilization occurs (no CTCAE grade change over 4 weeks).

#### **4.3.2.3 Guidelines for the follow-up of laboratory renal abnormalities**

In case of any occurrence of serum creatinine results of grade 2 or greater, tests must be performed weekly (or more frequently if clinically indicated) until the event resolves to  $\leq$  grade 1. Subsequent monitoring must be performed at least every 4 weeks.

In case of any occurrence of serum creatinine  $\geq$  grade 3, tests must be performed twice weekly (or more frequently if clinically indicated) until the event resolves to  $\leq$  grade 1. Subsequent monitoring must be performed at least every 4 weeks.

#### **4.3.2.4 Guidelines for the follow-up of laboratory pancreatic abnormalities**

In case of any occurrence of lipase or amylase increase to grade 3 or 4, both lipase and amylase must be monitored weekly (or more frequently if clinically indicated) until the event resolves to  $\leq$  grade 1 (or to baseline).

After resumption of dosing, monitoring must be continued weekly (or more frequently if clinically indicated) for one additional cycle (i.e. 4 weeks). If there is no recurrence of  $\geq$  grade 2 amylase or lipase elevations during this period, subsequent monitoring must be performed every 4 weeks.

Patients who discontinue study treatment due to pancreatic toxicity must be monitored weekly (or more frequently if clinically indicated) until the event resolves to  $\leq$  grade 1 or stabilization occurs (no CTCAE grade change over 4 weeks).

If amylase and/or lipase elevations are accompanied by new or progressive unexplained abdominal symptoms such as severe pain or vomiting, withhold ceritinib, then perform diagnostic procedures (e.g., abdominal CT scan or ultrasound) to exclude pancreatic pathology.

See also dose modification guidelines described in Table 4-3.

#### **4.3.2.5 Guidelines for monitoring pneumonitis**

Monitor patients for pulmonary symptoms indicative of pneumonitis. In addition, withhold ceritinib for acute onset of new or progressive unexplained pulmonary symptoms, such as dyspnea, cough and fever and during diagnostic workup for pneumonitis/ILD.

#### **4.3.2.6 Guidelines for the treatment of study drug induced diarrhea**

The investigator should consider/investigate potential concomitant medication, food or comorbidity driven causes of diarrhea (including infectious causes) and remedy these causes if possible (e.g. discontinuation of concomitant medication, dietary modification, treatment of comorbidity).

The patient should be monitored for signs of dehydration and instructed to take preventive measures against dehydration as soon as diarrhea occurs. Antidiarrheal medication must be initiated at the first sign of abdominal cramping, loose stools or overt diarrhea. Concomitant medication for the treatment of diarrhea should follow local practice and the investigator's best judgment and may follow "the recommended guidelines for the treatment of cancer treatment-induced diarrhea" (Benson et al 2004).

For example:

- For uncomplicated diarrhea (grade 1 or 2 without complicating signs or symptoms), loperamide given at a standard dose (e.g. initial administration of 4 mg, then 2 mg every 2-4 hours, maximum of 16 mg/day), along with oral hydration and dietetic measures should be considered.
- For complicated diarrhea (all grade 3 or 4, grade 1-2 with complicating signs or symptoms - moderate to severe cramping, decreased performance status, fever, neutropenia, frank bleeding or dehydration), management should involve intravenous (IV) fluids, and consider treatment with octreotide (at starting dose of 100 to 150  $\mu$ g sub-cutaneous tid or 25 to 50  $\mu$ g IV) and antibiotics (e.g. fluoroquinolone) should be given.
- Dose adaptation of ceritinib in case of treatment related diarrhea must follow the guidelines presented above in the Criteria for interruption and re-initiation of ceritinib Treatment table.

#### **4.3.2.7 Guidelines for the treatment of study drug induced nausea and vomiting**

Nausea and vomiting are among the most frequently reported AEs following treatment with ceritinib and patients must therefore be closely monitored for the appearance of these AEs.

The investigator should consider/investigate potential concomitant medication, food or comorbidity driven causes of nausea and/or vomiting and remedy these causes if possible (e.g. discontinuation of

concomitant medication, dietary modification, treatment of comorbidity). Adjusting the time of ingestion of ceritinib may influence perception and management of nausea (eg. taking it at bedtime).

Individualized supportive and anti-emetic treatment should be initiated, as appropriate, at the first signs and/or symptoms of these AEs. In patients with vomiting, the patient should be monitored for signs of dehydration and instructed to take preventive measures against dehydration. Concomitant medication for the treatment of nausea and/or vomiting should follow local practice and the investigator's best judgment. For moderate emetogenic drugs, such as ceritinib, International Guidelines for anti-emetic treatment recommend early treatment with 5-HT3-receptor antagonists (5-HT3RAs).

- Dose adaptation of ceritinib in case of treatment related nausea and/or vomiting must follow the guidelines presented above in the Criteria for interruption and re-initiation of ceritinib Treatment table.

